## 7. DISCONTINUATION OF STUDY INTERVENTION AND PARTICIPANT DISCONTINUATION/WITHDRAWAL

### 7.1. Discontinuation of Study Intervention

A participant's study intervention must be discontinued if:

- The participant withdraws consent to receive study intervention.
- The investigator believes that for safety reasons or tolerability reasons (eg, AE) it is in the best interest of the participant to discontinue study intervention.
- The participant becomes pregnant or plans to become pregnant within the study period. Refer to Appendix 5 [Section 10.5].
- A systemic opportunistic infection.
- The participant is unable to adhere to the study visit schedule or comply with protocol requirements.
- The participant is deemed ineligible according to the following TB screening criteria:
  - A diagnosis of active TB is made.
  - A participant has symptoms suggestive of active TB based on follow-up assessment questions and/or physical examination or has had recent close contact with a person with active TB and cannot or will not continue to undergo additional evaluation.
  - A participant undergoing evaluation has a chest radiograph with evidence of current active TB and/or a positive QuantiFERON®-TB test result and/or 2 indeterminate QuantiFERON®-TB test results on repeat testing (refer to Section 8.2.11) (and/or a positive tuberculin skin test result in countries in which the QuantiFERON®-TB test is not approved/registered or the tuberculin skin test is mandated by local health authorities).
  - The frequency of TB testing can be increased depending on local health authority requirements. Note: In Ukraine, while the QuantiFERON-TB® test is not approved/registered, it is acceptable, and an additional tuberculin skin test is not required.
  - A participant receiving treatment for latent TB discontinues this treatment prematurely or is noncompliant with the therapy.
- The participant has a serious adverse reaction that is temporally related to an injection including a hypersensitivity reaction resulting in bronchospasm, wheezing and/or dyspnea that requires ventilatory support OR that results in symptomatic hypotension with a decrease in systolic blood pressure of 30% from a participant's baseline value or systolic blood pressure <90 mm Hg (Sampson 2006). In general, discontinuation of study intervention administration must be considered for participants who develop a severe injection-site reaction.

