- The participant has a reaction resulting in myalgia and/or arthralgia with fever and/or rash (suggestive of serum sickness and not representative of signs and symptoms of other recognized clinical syndromes) occurring 1 to 14 days after an injection of study intervention. These may be accompanied by other events including pruritus, facial, hand, or lip edema, dysphagia, urticaria, sore throat, and/or headache.

- The participant has a malignancy including squamous cell skin cancer. Consideration may be given to allowing participants who develop  $\leq 2$  basal cell skin cancers that are adequately treated with no evidence of residual disease to continue to receive study intervention, after consultation with Sponsor medical monitor or designee.
- The participant has severe liver test abnormalities that are not transient and are not explained by other etiologies, as described in Appendix 8 (Section 10.8).
- The Sponsor may elect to terminate the study at any time, and if the Sponsor decides not to continue development for any reason, study medication/drug will no longer be provided to any participants, including those in the LTE.

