### **7.1.1. Liver Chemistry Stopping Criteria**

Discontinuation of study intervention for abnormal liver tests is required by the investigator when a participant meets one of the conditions in Appendix 8A (Section 10.8) or in the presence of abnormal liver chemistries not meeting protocol-specified stopping rules if the investigator believes that it is in best interest of the participant.

Refer to Appendix 8B (Section 10.8) for follow-up assessments (and study intervention restart guidelines) following abnormal liver test results. Study Sponsor must provide written approval before study intervention is restarted.

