## 10.8. Appendix 8: Liver Safety: Suggested Actions and Follow-up Assessments

### A. STOPPING ALGORITHM

#### Liver Chemistry Stopping Criteria and Increased Monitoring Algorithm

Study intervention will be discontinued for a participant if liver chemistry stopping criteria are met.

- Must refer to Liver Safety Required Actions and Follow up Assessments section in the Appendix
- Report to sponsor in an expedited manner if possible Hy's Law case: ALT or AST  $\geq 3\times$ ULN and Total bilirubin  $\geq 2\times$ ULN (>35% direct) or INR>1.5\* and as an SAE if SAE criteria met

[figure not shown]
\*INR value not applicable to participants on anticoagulants

Abbreviations: ALT = alanine transaminase; AST = aspartate transaminase, INR = international normalized ratio; SAE = serious adverse event; ULN = upper limit of normal, Tbili = Total bilirubin.

Refer to Appendix [8B]: Follow-up Assessments.

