### Phase 3-4 Liver Chemistry Stopping Criteria and Follow-Up assessments

Liver Chemistry Stopping Criteria	
ALT or AST-absolute	ALT or AST $\geq$ 8xULN
ALT or AST-Increase	ALT or AST $\geq$ 5xULN but $<$ 8xULN persists for $\geq$ 2 weeks ALT or AST $\geq$ 3xULN but $<$ 5xULN persists for $\geq$ 4 weeks
Bilirubin	ALT or AST $\geq$ 3xULN and total bilirubin $\geq$ 2xULN
INR^2	ALT or AST $\geq$ 3xULN and international normalized ratio (INR) $>$ 1.5
Cannot Monitor	ALT or AST $\geq$ 5xULN but $<$ 8xULN and cannot be monitored weekly for $\geq$ 2 weeks ALT or AST $\geq$ 3xULN but $<$ 5xULN and cannot be monitored weekly for $\geq$ 4 weeks
Symptomatic	ALT or AST $\geq$ 3xULN associated with symptoms (new or worsening) believed to be related to liver injury or hypersensitivity

Suggested Actions, Monitoring, and Follow up Assessments	
Actions	Follow Up Assessments

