
 
• Immediately discontinue study intervention
 
• Report the event to the Sponsor within 24 hours
 
• Complete the hepatic event form and complete an SAE eCRF if the event also met the criteria for an SAE
 
• Perform follow-up assessments as described in the Follow up Assessment column
 
• Monitor the participant until liver chemistry test abnormalities resolve, stabilize, or return to baseline
 
 
MONITORING:
 
If ALT or AST <math>\geq</math>3xULN AND total bilirubin <math>\geq</math>2xULN or INR <math>></math>1.5:
 
 
• Repeat liver chemistry tests (include ALT, aspartate transaminase [AST], alkaline phosphatase, total bilirubin, direct bilirubin, and INR) and perform
 
	
 
• Viral hepatitis serology
 
• Obtain blood sample for pharmacokinetic (PK) analysis within 1 week of the event of ALT or AST <math>\geq</math>3xULN
 
• Obtain serum creatine phosphokinase (CPK), lactate dehydrogenase (LDH), gamma-glutamyltransferase [GGT], and glutamate dehydrogenase [GLDH], and serum albumin
 
• Fractionate bilirubin, if total bilirubin <math>\geq</math>2xULN
 
• Obtain complete blood count with differential to assess eosinophilia
 
• Record the appearance or worsening of clinical symptoms of liver injury, or hypersensitivity, on hepatic event form
 
• Record use of concomitant medications (including acetaminophen, herbal remedies, recreational drugs, and other over-the-counter medications)
 
• Record alcohol use on the hepatic event form
 

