### **Restart Following Transient Resolving Liver Chemistry Events Not Related to Study Intervention**

- Restart refers to resuming study intervention following liver chemistry events for which there are clear underlying causes (other than DILI) (eg, biliary obstruction, pancreatic events, hypotension, acute viral hepatitis). Furthermore, restart is not permitted following liver stopping event when the underlying cause was alcohol-related hepatitis. Approval by the sponsor for study intervention restart can be considered when:
  - The investigator requests consideration for study intervention restart if liver chemistry events have a clear underlying cause (eg, biliary obstruction, pancreatic events, hypotension, acute viral hepatitis) and liver chemistry tests have improved to normal or are within 1.5 x baseline and ALT or AST <3xULN.
  - Possible DILI has been excluded by the investigator and the study team. This includes the absence of markers of hypersensitivity (otherwise unexplained fever, rash, eosinophilia). Where a study intervention has an identified genetic marker associated with liver injury (eg, lapatinib, abacavir, amoxicillin/clavulanate), the presence of the marker should be excluded.
  - There is no evidence of alcoholic-related hepatitis.
  - IRB/IEC approval of study intervention restart has been obtained.

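### The Section 7.1 liver bullet limits the mandatory stop by duration and cause and cites Appendix 8, but neither Appendix 8 nor Section 7.1.1 sets these as general stopping conditions

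*Protocol*

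**What the plan says.** Three places in the protocol state when abnormal liver tests end dosing.

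- **Section 7.1.** The list opens with "A participant's study intervention must be discontinued if". Its liver entry reads: "The participant has severe liver test abnormalities that are not transient and are not explained by other etiologies, as described in Appendix 8".
- **Section 7.1.1.** "Discontinuation of study intervention for abnormal liver tests is required by the investigator when a participant meets one of the conditions in Appendix 8A". A second limb allows a stop below the thresholds on the investigator's judgement. Neither limb mentions duration or cause.
- **Appendix 8 (Section 10.8).** Part A says: "Study intervention will be discontinued for a participant if liver chemistry stopping criteria are met". The criteria table in part B gives the thresholds, and its action column begins "Immediately discontinue study intervention".

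Appendix 8 takes up transience and other causes in its restart section: "Restart refers to resuming study intervention following liver chemistry events for which there are clear underlying causes (other than DILI"). Restart needs sponsor approval, ethics committee approval and a separate signed consent. It is ruled out when the cause was alcohol-related hepatitis.

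The appendix also labels itself in two ways. Its title and action table call the actions suggested, while part A sends the reader to a section of required actions.

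**The concern.** The Section 7.1 bullet attributes its two qualifiers to Appendix 8. The appendix text that can be read does not use them to decide whether to stop. It uses them to decide whether dosing may resume after a stop. A site that treats Section 7.1 as the binding list and the appendix as guidance could conclude that a stop is not compulsory while duration and cause are being worked out.

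The first stake is safety. Section 2.3.1 names liver injury as a potential risk and describes one possible drug-induced case.

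The second stake is classification. Under the adjusted composite estimand (Protocol 9.4.2, SAP 5.3.4.2), discontinuing injections before Week 24 for a reason other than a Natural Disaster or Major Disruption is ICE 1 and makes the participant an ACR 20 non-responder. SAP Appendix 7 counts a clinically important hepatic disorder only if the event was serious or led to discontinuation, so the stopping rule partly sets that count too.

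**Working it through.** No calculation underlies the inconsistency itself, so the check sets the Section 7.1 bullet against each criterion in the Appendix 8B table.

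| Appendix 8B criterion | Must the abnormality persist? | Exempt if another cause? |
|---|---|---|
| ALT or AST at least 8xULN | No | No |
| 5 to <8xULN | Yes, 2 weeks | No |
| 3 to <5xULN | Yes, 4 weeks | No |
| At least 3xULN with bilirubin at least 2xULN | No | No |
| At least 3xULN with INR above 1.5 | No | No |
| 3 to <8xULN, weekly monitoring not possible | No | No |
| At least 3xULN with symptoms | No | No |

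Two details qualify the last column. The INR threshold is waived for participants on anticoagulants, which concerns the INR value and not the cause of the transaminase rise. The symptoms row requires symptoms thought to come from liver injury or hypersensitivity, but does not ask whether study drug caused the injury.

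**Duration.** The bullet and the table overlap for the two persistence rows. They differ for the others.

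**Cause.** The bullet and the table differ for every row.

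**Two cases built from the protocol's own examples:**

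1. ALT at least 8xULN with suspected acute viral hepatitis, which Appendix 8 names as a clear underlying cause. The Section 7.1 bullet alone does not mandate a stop. Section 7.1.1 and Appendix 8 do, and dosing may resume only through the restart process.
2. A threshold met because of alcohol-related hepatitis. This is another etiology, so the bullet alone does not mandate a stop. Under Appendix 8 dosing stops and restart is not permitted. The gap is widest here.

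**Scale on the primary endpoint.** With the planned arms, one reclassified participant changes a response rate by 1/250 = 0.40 percentage points (q4w) or 1/350 = 0.29 points (q8w or placebo). The planning difference is 60% − 35% = 25 points, and power exceeds 99% in every row of Protocol Table 6.

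**SAP.** The five liver categories in SAP 5.4.4.1 reproduce the Appendix 8B criteria, with bilirubin and INR merged, and do not carry the Section 7.1 qualifiers. The SAP does not say whether a liver stop followed by an approved restart is ICE 1. SAP 5.4.3 tabulates permanent discontinuation and dose interruption separately, but the ICE 1 definition does not draw that line.

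**The case against.** The strongest reply is that nothing in Section 7.1 permits dosing. Its list says *if*, not *only if*, so each bullet is a sufficient reason to stop, and another bullet covers any stop the investigator judges necessary for safety or tolerability. Section 7.1.1 is a subsection of the same text with an unqualified requirement, and the bullet itself points to Appendix 8. A careful site would read all three and stop. This stands, and it limits the defect to what the bullet says when read alone.

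It is also fair that Appendix 8 is not blind to duration. Two rows require persistence, and a monitoring algorithm with continued dosing covers 3 to <8xULN. This stands too.

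A further defence is that the bullet means the final outcome: events that are neither transient nor otherwise explained are roughly those for which restart would be refused. That reading is possible, but Section 7.1 does not say permanent discontinuation, and the alcohol case does not fit it.

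Several stronger inferences are tempting and not supported:

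- *The same event is stopped at one site and dosed at another.* The documents make this possible, not certain.
- *Sites could bypass the sponsor.* Appendix 8 requires a report within 24 hours and repeat tests within 24 hours or 24 to 72 hours, and Section 7.1.1 requires the sponsor's written approval before restart.
- *The q4w arm is especially exposed.* Section 2.3.1 links 100 mg q4w or higher to mild elevations, up to 3xULN, whereas the stopping thresholds start at 3xULN. It calls ALT above 5xULN and biochemical Hy's Law cases infrequent and confounded.
- *Some 5 to 19 participants are affected.* That follows from assuming that 0.5% to 2% of 950 meet a threshold (4.75 to 19). The rates have no source in the documents, and they count everyone at a threshold, not only those with a transient or otherwise explained event before Week 24 at a site that misreads the bullet.

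**Conclusion.** Wrong as written: a safety rule stated inconsistently. The Section 7.1 bullet misdescribes the appendix it cites. It differs from Section 7.1.1 and Appendix 8 on cause for every criterion, and on duration for all but the two persistence rows. No precedence rule settles which text governs, and the mixed labels of suggested and required leave the standing of the appendix open.

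The consequence is a foreseeable risk of uneven handling. Its frequency cannot be estimated from the documents. The reason to correct it is clarity of a safety stop, not protection of the efficacy result: at 0.29 to 0.40 percentage points per participant against a 25-point planning difference, a few reclassified participants would not plausibly decide the primary comparison.

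The conclusion rests on the visible text. The Appendix 8A algorithm figure is not shown, so a qualifier drawn there could not be checked. It takes no position on which stopping rule is clinically right.

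**What to change.** The sponsor's medical team should reconcile Section 7.1, Section 7.1.1 and Appendix 8:

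1. State the liver stopping trigger in one place and have the other two only cross-refer to it.
2. Say explicitly whether a transient course and another etiology bear on stopping, on restart, or on both.
3. Settle whether the Appendix 8 actions are suggested or required, and label them the same way throughout.
4. State in the SAP whether a liver stop followed by an approved restart counts as ICE 1.

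SAP 5.4.4.1 already uses the Appendix 8 criteria and needs no change unless the reconciliation alters those criteria.

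The cost is a short wording correction at the next protocol amendment, a clarification letter to sites and one sentence in the SAP. No further tests, visits or participants are needed.

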**Discontinuation of a participant's study intervention should be considered under the following conditions:**

- If the participant initiates treatment with prohibited therapies, the medical monitor or designee should be notified for possible discontinuation of study intervention.
- Recurrent or chronic serious infection.
- The participant develops a serious infection, including but not limited to sepsis or pneumonia. Note: Any serious infection should be discussed with the medical monitor or designee, and study intervention should be withheld until the clinical assessment is complete.
- Discontinuation of study treatment should be considered for participants who report suicidal Ideation level 4 (some intent to act, no plan), Ideation level 5 (specific plan and intent), or any suicidal behavior (actual suicide attempts, interrupted attempts, aborted attempts, or preparatory actions) on a postbaseline (after Week 0) eC-SSRS assessment. Discussion of such participants with the medical monitor or designee is required.
- The participant develops a severe injection-site reaction, but not meeting criteria specified above.

If a participant discontinues study intervention for any reason before the end of the double-blind phase, they should be encouraged to continue in the study.

Study intervention assigned to the participant who discontinued study intervention may not be assigned to another participant. Additional participants may be entered to ensure the protocol-specified number of patients complete the study.

### **7.1.1. Liver Chemistry Stopping Criteria**

Discontinuation of study intervention for abnormal liver tests is required by the investigator when a participant meets one of the conditions in Appendix 8A (Section 10.8) or in the presence of abnormal liver chemistries not meeting protocol-specified stopping rules if the investigator believes that it is in best interest of the participant.

Refer to Appendix 8B (Section 10.8) for follow-up assessments (and study intervention restart guidelines) following abnormal liver test results. Study Sponsor must provide written approval before study intervention is restarted.

## 7.2. Participant Discontinuation/Withdrawal from the Study

A participant will be withdrawn from the study for any of the following reasons:

- Lost to follow-up
- Withdrawal of consent
- Death
- Sponsor decision (eg, participating in any other clinical study with an investigational agent)

When a participant withdraws before study completion, the reason for withdrawal is to be documented in the eCRF and in the source document. If the reason for withdrawal from the study is withdrawal of consent, then no additional assessments are allowed.

### **Discontinuation of Study Drug Intervention**

If a participant discontinues study drug intervention, they should be encouraged to return for all remaining core study visits; It is particularly important to return for all visits through Week 24.

#### ***Prior to Week 24***

If a participant discontinues study intervention before the Week 24 visit, the participant should return for all visits through Week 24. The final safety assessments will be conducted at the next scheduled visit that occurs approximately 12 weeks after the last dose of study administration of study intervention. If a participant discontinues before the Week 24 visit and after the Week 12 study intervention administration, the participant should return for the Week 24 visit and also 12 weeks after the last administration of study intervention for a final safety visit.

For participants who discontinue study intervention prior to Week 24, radiographs of the hands and feet should still be performed at the Week 24 visit.

#### ***At or After Week 24 and Prior to Week 48***

If a participant discontinues study intervention at or after Week 24 and is unable to return for all visits through Week 48, the final efficacy visit should occur at the time of discontinuation or as soon as possible and all assessments under the Week 48/final efficacy should be performed including radiographs of hands and feet, (unless another set of radiographs has been obtained within the past 6 weeks) with the exception of study intervention administration. The participant should also return for a final safety visit approximately 12 weeks after the last study intervention administration.

#### ***At or After Week 48 and Prior to Week 156***

If a participant discontinues study intervention at or after Week 48 and is unable to return for all visits through Week 156, the final efficacy visit should occur at the time of discontinuation or as soon as possible and all assessments under the Week 156/final efficacy should be performed including radiographs of hands and feet, (unless another set of radiographs has been obtained within the past 6 weeks) with the exception of study intervention administration. The participant

should also return for a final safety visit approximately 12 weeks after the last study intervention administration.

## **Withdrawal of Consent**

A participant declining to return for scheduled visits does not necessarily constitute withdrawal of consent. Alternate follow-up mechanisms that the participant agreed to when signing the consent form apply as local regulations permit.

Withdrawal of consent should be an infrequent occurrence in clinical studies (Rodriguez 2015), therefore, prior to the start of the study the Sponsor and the investigator should discuss and reach a clear understanding of what constitutes withdrawal of consent in the context of the available reduced follow-up mechanisms listed.

## **Circumstances for Reduced Follow-up**

In the situation where a participant may be at risk for withdrawal of consent and is unable to return for scheduled visits at the protocol-defined frequency, the investigator may consider options for reduced follow-up with consultation of the Sponsor/designee and/or medical monitor. These may include (as local regulations permit):

- Less frequent clinical visits
- Telephone, email, letter, social media, fax, or other contact with:
  - participant
  - relatives of the participant
  - participant's physicians (general or specialist)
- Review of any available medical records

Details regarding these contacts must be properly documented in source records including responses by participants.

